### **9.7 Missed Doses**

If a subject misses a dose and recalls the missed dose within 6 hours, the subject should take his/her dose with food. If more than 6 hours have elapsed after his/her usual dosing time, the subject should skip that dose and resume his/her normal schedule for the following dose. For example;

- If the morning dose of study drug should have been taken at approximately 08:00, and the subject remembers at 12:00 that he/she forgot to take his/her dose, he/she should take the dose with food as soon as possible.
- If the morning dose of study drug should have been taken at approximately 08:00, and greater than 6 hours have elapsed beyond the scheduled dosing time (i.e., the time is past 14:00), the subject would resume dosing with the evening dose at approximately 20:00.

### **9.8 Removal of Subjects**

Subjects may withdraw from the study at any time at their own request. Subjects may be withdrawn from study drug treatment at any time at the discretion of the investigator or Vertex for safety, behavior, noncompliance with study procedures, or administrative reasons. If a subject has been withdrawn from study drug treatment, the subject will continue to be followed, provided the subject has not withdrawn consent.

If a subject does not return for a scheduled visit, reasonable effort will be made to contact the subject. In any circumstance, reasonable effort will be made to document subject outcome. The investigator will inquire about the reason for withdrawal, request that the subject return all unused investigational product(s), request that the subject return for a Safety Follow-up Visit, if applicable (see [Section 9.1.3](#)), and follow up with the subject regarding any unresolved AEs.

If the subject withdraws consent for the study, no further evaluations should be performed, and no additional data should be collected. Vertex may retain and continue using the study data and samples after the study is over, and may use the samples and information in the development of

the study compound, and for other drugs and diagnostics, in publications and presentations, and for education purposes. If the subject withdraws from the study, the study data and samples collected will remain part of the study. A subject will not be able to request the withdrawal of his/her information from the study data. A subject may request destruction of the samples collected from him/her during the study as long as those samples can be identified as his/her samples.

### **9.9 Replacement of Subjects**

Subjects who withdraw or are withdrawn during the study drug Treatment Period will not be replaced.

## **10 STUDY DRUG INFORMATION AND MANAGEMENT**

### **10.1 Preparation and Dispensing**

Study drug may be dispensed only under the supervision of the investigator or an authorized designee and only for administration to the study subjects.

### **10.2 Packaging and Labeling**

Study drug tablets will be supplied in blister cards by Vertex. Study drug labeling will be in compliance with applicable local and national regulations. Additional details regarding packaging, labeling, and dispensing for TEZ and IVA will be included in the Pharmacy Manual.

### **10.3 Study Drug Supply, Storage, and Handling**

Blister cards must be stored at room temperature according to [Table 10-1](#) and to the instructions provided in the Pharmacy Manual. While at the clinical site, the investigator, or an authorized designee (e.g., a licensed pharmacist), will ensure that all investigational product is stored in a secured area, under recommended storage conditions, and in accordance with applicable regulatory requirements. To ensure adequate records, all study drugs will be accounted for in [Section 10.4](#).

Instructions regarding the storage and handling of study drug after dispensation to subjects will be provided to sites in the Pharmacy Manual.

**Table 10-1 Identity of Study Drugs, Dosage, and Storage**

Drug Name	Formulation/Route	Dosage	Storage Condition
TEZ/IVA	Fixed-dose combination tablet; oral	TEZ 50 mg/IVA 75 mg or TEZ 100 mg/IVA 150 mg	≤25°C (77°F) with excursions to 30°C (86°F)
IVA	Tablet; oral	75 mg or 150 mg	≤25°C (77°F) with excursions to 30°C (86°F)
TEZ/IVA-matching placebo	Fixed-dose combination tablet; oral	TEZ 0 mg/IVA 0 mg	≤25°C (77°F) with excursions to 30°C (86°F)
IVA-matching placebo	Tablet; oral	IVA 0 mg	≤25°C (77°F) with excursions to 30°C (86°F)

#### 10.4 Drug Accountability

The pharmacist or designated study site staff will maintain information regarding the dates and amounts of (1) study drug received; (2) study drug dispensed to the subjects; and (3) study drug returned by the subjects. Subjects will be instructed to return all used and unused materials associated with the study drug to the site. These materials will be retained at the site according to instructions provided by Vertex or its designee until inventoried by the study monitor. The study monitor will review study drug records and inventory throughout the study.

#### 10.5 Disposal, Return, or Retention of Unused Drug

The study site staff or pharmacy personnel will retain all materials returned by the subjects until the study monitor has performed drug accountability. At the end of the study, the study monitor will provide instructions as to the disposition of any unused investigational product. If the study monitor authorizes destruction at the study site, the investigator will ensure that the materials are destroyed in compliance with applicable environmental regulations, institutional policy, and any special instructions provided by Vertex. Destruction will be adequately documented.

#### 10.6 Compliance

To ensure treatment compliance, the investigator or designee will supervise all study drug dosing that occurs at the site. At each visit, site personnel will review that the subject is compliant with study drug dosing and remind the subject of study drug dosing requirements. Compliance will also be assessed by ongoing study drug count.

If a subject demonstrates continued noncompliance of study drug dosing despite educational efforts, the investigator will contact the medical monitor to discuss discontinuation of the subject from the study.

## 10.7 Discontinuation of Study Participation

If after review of a marketing application, local health authorities decline to approve, or if clinical benefit is not demonstrated for the use of TEZ/IVA for the treatment of CF in a corresponding population aged  $\geq 12$  years, pediatric subjects enrolled in Study 115, subjects with the relevant *CFTR* genotypes may be discontinued after communication to investigators and IRBs/IECs of the risks/benefits related to the safety and efficacy observed for the subset of subjects.

If the *CFTR* screening genotype result is not received before enrollment and a previous *CFTR* genotype lab report is used to establish eligibility, enrolled subjects whose screening genotype does not confirm study eligibility must be discontinued from the study and complete an ETT and/or a Safety Follow-up Visit as described in [Section 9.1.3](#) and [Section 9.1.4](#).

## 10.8 Blinding and Unblinding

This is a double-blind study.

### 10.8.1 Blinding

All study personnel will be blinded to subject treatment assignments except for the following individuals:

- Any site personnel for whom this information is important to ensure the safety of the subject in the event of a life-threatening medical emergency
- Any site personnel for whom this information is important to ensure the safety of the subject and the fetus in the event of a pregnancy
- The unblinded site monitor and unblinded trip report reviewer
- An unblinded pharmacist at the contract research organization (CRO) for dispensing study drug
- Vertex Global Patient Safety (GPS) and Regulatory Affairs personnel to satisfy serious adverse event (SAE) processing and reporting regulations
- External vendor (unblinded) statistician preparing the final (production) randomization list who is not part of the study team
- Vertex IXRS Management for IXRS oversight and system administration
- Vertex Clinical Supply Chain
- The bioanalytical CRO laboratory/vendor personnel managed by Vertex Bioanalysis
- The Vertex bioanalytical personnel responsible for reviewing raw data from the bioanalytical CRO, who is not a member of the SET (the Vertex bioanalytical SET member will continue to be blinded).

Vertex medical monitor may, for matters relating to safety concerns, unblind individual subjects at any time.

### 10.8.2 Unblinding

At the initiation of the study, the study site will be instructed on the method for breaking the blind. The unblinding method will be either a manual or electronic process.

Unblinding of the individual subject's treatment by the investigator will be limited to medical emergencies or urgent clinical situations in which knowledge of the subject's study treatment is necessary for clinical management. In such cases, investigators will use their best judgment as to whether to unblind without first attempting to contact the medical monitor to discuss and agree to the need for unblinding. If investigators deem it not necessary to unblind immediately, they will first attempt to contact the medical monitor to discuss and agree to the need for unblinding. If investigators have tried but are unable to reach the medical monitor, they will use their best judgment, based on the nature and urgency of the clinical situation, and may proceed with unblinding without having successfully reached and discussed the situation with the medical monitor. In case of emergency, the treating physician will have the final decision and unilateral right for unblinding.

Contact information for the medical monitor (or appropriate backup) will be provided in a separate document.

In addition, the Vertex Medical Information Call Center ( [REDACTED] ) will answer calls 24 hours a day, 7 days a week, 365 days of the year, and will triage these calls to the study medical monitor or appropriate backup.

If a subject's treatment assignment has been unblinded for a medical emergency or urgent clinical situation, the medical monitor will be notified within 24 hours of the unblinding event. The reason and the date of the unblinding will be documented clearly in the subject's study file. Information about the treatment assignment obtained from the unblinding will be maintained in a secure location with controlled access and will not be shared with the sponsor (Vertex), CRO, or any site personnel (other than the physician treating the subject). In addition, the investigator will consider whether the clinical event that prompted unblinding will be considered an SAE, according to the regulatory definitions or criteria for SAEs, and if so, submit an SAE report to Vertex GPS or designee, per [Section 13.1.2.3](#).

Vertex GPS or designee will also unblind any SAE reports in compliance with regulatory reporting requirements. In addition, Vertex may, for matters relating to safety concerns, unblind individual subjects at any time.

## **11 ASSESSMENTS**

### **11.1 Timing of Assessments**

The following assessments must be performed in the order specified below when more than 1 assessment is required at a particular time point:

1. The CFQ-R should be completed before the start of any other assessments scheduled at that visit.

3. ECGs will be performed before dosing and before any other procedures that may affect heart rate (e.g., blood draws).

4. The MBW assessment should be performed before spirometry.

5. Blood sampling for clinical laboratory assessments at all visits, except the Day 1 Visit, may be conducted at any time during the visit.

[REDACTED]

The schedule of assessments is shown in [Table 3-1](#).

## **11.2 Subject and Disease Characteristics**

Subject and disease characteristics include the following: demographics, medical history, height, and weight.

## **11.4 Efficacy**

### **11.4.1 Lung Clearance Index**

LCI derived from N2-MBW testing will be conducted at visits specified in [Table 3-1](#) to evaluate the effect of TEZ/IVA on lung ventilation inhomogeneity. LCI2.5 represents the number of lung turnovers required to reduce the end tidal inert gas concentration to 1/40th of its starting value,

[REDACTED]

Pre-bronchodilator MBW testing is defined as MBW testing performed for subjects who have

- withheld their short-acting bronchodilator (e.g., albuterol) or anticholinergic (e.g., Atrovent®) for more than 4 hours before the MBW testing;

- withheld their long-acting bronchodilator (e.g., salmeterol) more than 12 hours before the MBW testing; and
- withheld their once-daily, long-acting bronchodilator (e.g., tiotropium bromide [Spiriva®]) for more than 24 hours before the MBW testing.

MBW testing should be performed “pre-bronchodilator.” MBW testing must be performed before dosing, unless noted otherwise. In the event that a subject forgets to withhold bronchodilator(s), MBW testing should be performed according to the following:

- If a subject's Day 1 MBW testing is pre-bronchodilator, but on a subsequent visit, the subject forgets to withhold bronchodilator use, post-bronchodilator MBW testing will be obtained for that visit only, and the visit will not be rescheduled.
- If on Day 1, the subject forgets to withhold his/her dose of bronchodilator, MBW testing should be performed post-bronchodilator and all subsequent MBW testing (according to the Schedule of Assessments detailed for LCI in [Table 3-1](#)) should be performed post-bronchodilator.
- Subjects and their parent/caregiver should not be informed of their study-related LCI results during the Treatment Period.

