**Table 3-1 Study VX16-661-115: Screening, Treatment Period, Early Termination of Treatment, and Safety Follow-up**

Event/Assessment a	Treatment Period					Early Termination of Treatment (ETT) Visit b	Safety Follow-up Visit (4 Weeks [± 7 Days] After Last Dose of Study Drug) c
	Screening Period Day -28 to Day -1	Day 1	Week 2 (± 3 Days)	Week 4 (± 5 Days)	Week 8 (± 5 Days) d		
Urinalysis o	X	X			X	X	X
Lipid panel o		X p			X	X	X
Vitamin levels o		X p			X	X	X
Serum chemistry o	X	X p	X	X	X	X	X
Hematology o	X	X p	X		X	X	X
Coagulation studies o	X				X	X	X
Multiple-breath washout (MBW) s	X	X	X	X	X		
Spirometry t	X	X	X	X	X	X	X
Meal or snack at clinic		X	X	X	optional		
Study drug count			X	X	X	X	

o See Section 11.5.2 for details.

p Blood samples to be collected predose on Day 1. At all other scheduled visits, these samples will be collected at any time during the visit.

s The MBW assessment will be performed in multiple replicates and before study drug dosing (see Section 11.4.1 and the Study Reference Manual). MBW should be performed pre-bronchodilator and will be performed before the spirometry assessment.

t At the Screening Visit, spirometry may be performed pre- or post-bronchodilator. At all visits during the Treatment Period, spirometry must be performed for all subjects before dosing and should be performed pre-bronchodilator. On Day 1 and Week 2, additional spirometry will be performed at 2 (± 30 minutes) and 4 hours (± 30 minutes) postdose. If more than 1 spirometry assessment is required at a visit, bronchodilators should be withheld until the last scheduled spirometry assessment is completed. If study drug is not administered on the day of the visit (i.e., study drug interruption or permanent discontinuation of study drug) the assessment will only be collected once.

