**Table 9-1 Lifestyle Guidelines and Study Restrictions**

Restricted Medication/Food	Study Period	
	Screening Period	Treatment Period
Certain fruits and fruit juices (grapefruit, grapefruit juice, Seville oranges, marmalade)	None allowed within 14 days before the first dose of study drug	None allowed through the Safety Follow-up Visit
Moderate and strong CYP3A inducers	None allowed within 14 days before the first dose of study drug	None allowed through the Safety Follow-up Visit
Strong and moderate CYP3A inhibitors (except Ciprofloxacin)	None allowed within 14 days before the first dose of study drug	None allowed through the Safety Follow-up Visit
Investigational or physician-prescribed Orkambi (LUM/IVA) or Kalydeco	None allowed within 28 days before the Day 1 Visit	None allowed through the last dose of study drug
Commercially available TEZ/IVA	None allowed within 28 days before the first dose of study drug	None allowed through the last dose of study drug
Other investigational drugs or devices	None allowed within 30 days or 5 half-lives before screening, or time determined by local requirements; whichever is longer	None allowed through the Safety Follow-up Visit

Note: The use of restricted medication in subjects with a medical need will be addressed on a case-by-case basis with the medical monitor or authorized designee. See the Study Reference Manual for a more complete list of medications prohibited/restricted in the study.

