## 9.5 Prior and Concomitant Medications

Subjects will abstain from all restricted concomitant medications as described in the exclusion criteria ([Section 8.2](#)).

Information regarding all prior and concomitant medications, including the subject's CF medications, other medications, and herbal and naturopathic remedies administered from

4 weeks before the Screening Period through the Safety Follow-up Visit will be recorded in each subject's source documents and electronic case report form (eCRF).

- It is recommended that subjects remain on their stable medication regimen for CF from 4 weeks before Day 1 through Week 8 or, if applicable, through the Safety Follow-up Visit. Stable medication regimen is defined as the current medication regimen for CF (except for commercially available CFTR modulators) that subjects have been following for at least 4 weeks before Day 1. Subjects must not initiate long-term treatment with new medication from 28 days before Day 1 through the Safety Follow-up Visit unless discussed and approved by the Vertex medical monitor. Guidelines for stable medication regimens for CF are as follows:
  - Subjects who are taking daily inhaled tobramycin or other chronically inhaled antibiotics should remain on that regimen throughout the study.
  - Subjects who are on inhaled cycling antibiotics should continue on their prior schedule. The timing of the first dose of study drug should be synchronized as closely as possible to the first day of inhaled cycling antibiotics in the cycle.
  - Subjects who alternate 2 different antibiotics monthly should remain on the same schedule during the study. The timing of the first dose of study drug should be synchronized as closely as possible to the first day of 1 of the inhaled alternating antibiotics.
- Subjects may receive doses of prednisone (or prednisolone) of up to 10 mg/day (chronically), or prednisone (or prednisolone) 60 mg qd for up to 5 days with tapering down to 10 mg/day within 2 weeks, without prior approval of the medical monitor.
- Information about bronchodilator use during the study will be collected and documented. Subjects who are using a bronchodilator must have their spirometry assessments performed according to the guidelines provided in [Section 11.4.2](#).

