#### 11.4.2 Spirometry

Spirometry will be performed according to the ATS/ERS Guidelines at the time points noted in [Table 3-1](#) according to the additional guidelines that follow.

Pre-bronchodilator spirometry is defined as spirometry testing performed for subjects who have

- withheld their short-acting bronchodilator (e.g., albuterol) or anticholinergic (e.g., Atrovent) for more than 4 hours before the spirometry assessment;
- withheld their long-acting bronchodilator (e.g., salmeterol) more than 12 hours before the spirometry assessment; and
- withheld their once-daily, long-acting bronchodilator (e.g., tiotropium bromide [Spiriva]) for more than 24 hours before the spirometry assessment.

All spirometry assessments should be performed “pre-bronchodilator.” During the Treatment Period, spirometry assessments must be performed before dosing, unless noted otherwise. In the event that a subject forgets to withhold bronchodilator(s), spirometry should be performed according to the following:

- If a subject's Day 1 spirometry is pre-bronchodilator, but on a subsequent visit, the subject forgets to withhold bronchodilator use, a post-bronchodilator spirometry will be obtained for that visit only, and the visit will not be rescheduled.
- If on Day 1, the subject forgets to withhold his/her dose of bronchodilator, spirometry should be performed post-bronchodilator and all subsequent spirometric measurements (according to the Schedule of Assessments detailed in [Table 3-1](#)) should be performed post-bronchodilator.
- Each spirometry assessment will be recorded in the source documents as pre-bronchodilator or post-bronchodilator.

The parameters listed below will be normalized using the standards of GLI.

- FEV1 (L)
- Forced vital capacity (FVC) (L)
- FEV1/FVC (ratio)
- Forced expiratory flow, midexpiratory phase (FEF25%-75%) (L/s)

All sites will be provided with spirometers and associated materials to be used for all study assessments by the central spirometry service. Spirometry data will be transmitted to a centralized spirometry service for quality review.

Subjects and their parent/caregiver should not be informed of their study-related spirometry results during the Treatment Period.

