7.2 Sample Size and Power

The sample size of this study is driven by demonstrating that the treatment effect of TEZ/IVA excludes a maximum possible placebo effect, which is based on a within-group comparison (change from baseline in LCI_{2.5} in subjects on TEZ/IVA). If the corresponding 2-sided 95% CI of the change from baseline in LCI_{2.5} in subjects on TEZ/IVA excludes the pre-defined maximum possible placebo effect, it will be considered that the study has achieved its primary objective.

A placebo effect is not expected with LCI, because clinical data from other Vertex CFTR modulator studies consistently demonstrated a worsening of lung function (i.e., an increase from baseline in LCI) in the absence of CFTR modulator treatment. Study VX14-809-109 (Study 809-109) evaluated treatment with LUM/IVA in F/F subjects aged 6 through 11 years using change from baseline in LCI as the primary efficacy endpoint and provided the most relevant clinical LCI data available in the younger age group of CF subjects. In Study 809-

109, the placebo group had a mean worsening in LCI_{2.5} of 0.08 units with an SD of 1.41 (higher numbers indicate a worsening of an LCI measurement); the one-sided 90% lower bound was -0.10 and is used as an estimate for the pre-defined maximum possible placebo effect for Study 115.

Accounting for a 10% dropout rate, approximately 40 subjects in the TEZ/IVA group will provide at least 90% power to exclude -0.10 if the true mean change is -0.9 with an SD of 1.41 using a two-sided alpha of 0.05. The current estimate of the maximum possible placebo effect is based on Study 809-109 placebo data in pediatric F/F subjects with CF.

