9.3.1 Analysis of the Primary Efficacy Variable

The primary efficacy endpoint is the absolute change in $LCI_{2.5}$ from baseline through Week 8. The objective of the primary efficacy endpoint analysis is to demonstrate that the mean absolute change from baseline in $LCI_{2.5}$ through Week 8 excludes a pre-defined maximum placebo effect in subjects in the TEZ/IVA group.

The primary analysis will be performed using a restricted maximum likelihood (REML)-based mixed-effect model for repeated measures (MMRM) for the subjects in the TEZ/IVA treatment group in the FAS population. The model will include absolute change from baseline in $LCI_{2.5}$ (including all measurements up to Week 8 [inclusive], both on treatment measurements and measurements after treatment discontinuation) as the dependent variable, and visit (as a class variable) as a fixed effect, with adjustment for mutation group based on the second *CFTR* allele (F/F and F/RF) and baseline $LCI_{2.5}$ (continuous) value as covariates, and subject as a random effect. An unconstructed covariance structure will be used to model the within-subject errors. If the model fails to converge, a compound symmetry covariance structure will be considered. The degrees of freedom of the denominator will be approximated by the Kenward-Roger's method².

The primary results obtained from the model will be the estimated average treatment effect through Week 8 in $LCI_{2.5}$ for subjects on TEZ/IVA. The corresponding LS mean, standard error (SE), 95% CI, and *p*-value will be provided. If the upper bound of the 95% CI is below the pre-defined maximum possible placebo effect, which was specified in the protocol, it will be considered that the study has achieved its primary objective. Summary statistics for change from baseline in $LCI_{2.5}$ through Week 8, and at each visit will also be provided for subjects in the TEZ/IVA treatment group by mutation groups and overall.

For F/F subjects in the placebo treatment group, summary statistics will be provided for change from baseline in LCI_{2.5} through Week 8, and at each visit.

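### Do LCI values taken after a forgotten bronchodilator hold compromise the one-arm primary analysis?

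*Protocol*

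**What the plan says.** Protocol 11.4.1 asks for multiple-breath washout (MBW) before bronchodilator use, with withholding times of 4, 12 and 24 hours by drug class. It covers two lapses:

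- **Day 1 pre-bronchodilator, later visit not withheld:** "post-bronchodilator MBW testing will be obtained for that visit only, and the visit will not be rescheduled".
- **Day 1 not withheld:** that test is post-bronchodilator, and so should be "all subsequent MBW testing (according to the Schedule of Assessments detailed for LCI in" Table 3-1.

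Footnote s to Table 3-1 states that "MBW should be performed pre-bronchodilator and will be performed before the spirometry assessment", and it refers to the Study Reference Manual for MBW detail. Protocol 11.4.2 adds for spirometry: "Each spirometry assessment will be recorded in the source documents as pre-bronchodilator or post-bronchodilator". The readable MBW section has no such sentence, but Protocol 9.5 provides for bronchodilator use to be documented during the study.

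The primary model (SAP 9.3.1; Protocol 12.3.3.1) is fitted to TEZ/IVA subjects only. It takes change in LCI2.5, "including all measurements up to Week 8 [inclusive], both on treatment measurements and measurements after treatment discontinuation", with terms for visit, mutation group and baseline LCI2.5. Success requires the upper 95% confidence limit to lie below -0.10. SAP 7.2 says that about 40 TEZ/IVA subjects "will provide at least 90% power to exclude -0.10 if the true mean change is -0.9 with an SD of 1.41", allowing for 10% dropout.

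**The concern.** The plan restores comparability when Day 1 is post-bronchodilator but accepts a mismatch when Day 1 is pre-bronchodilator. Mismatches therefore run mainly one way, post against pre, and need not average out. In a two-arm comparison a shift common to both arms would largely cancel. Here there is one arm and a fixed threshold, so nothing in the primary test cancels it. If a bronchodilator lowers LCI, some of the apparent improvement would not belong to TEZ/IVA, and the chance of declaring success at a true change of -0.10 would exceed 2.5%.

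The baseline definition, the visit windows and the missing-data rule do not mention bronchodilator state. There is no per-protocol set, and no sensitivity analysis of the primary endpoint appears in the readable text. The documents also do not say how the Study 809-109 placebo group, the source of -0.10, handled such tests.

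A neighbouring question concerns other treatment after stopping study drug. For CFTR modulators Table 9-1 says "None allowed through the last dose of study drug", while Protocol 9.5 says "Subjects must not initiate long-term treatment with new medication from 28 days before Day 1 through the Safety Follow-up Visit" unless the medical monitor approves. Efficacy values taken after such a start also enter the models.

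**Working it through.** **Inputs from the documents.** Margin -0.10, true mean change -0.9, SD 1.41, two-sided alpha 0.05, 10% dropout, about 40 on TEZ/IVA (SAP 7.2). Table 12-1 of the protocol targets 40 F/F + 12 F/RF = 52 on TEZ/IVA. Post-baseline visits are Weeks 2, 4 and 8, so 52 x 3 = 156 planned tests.

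**The plan's own figure.** This is a one-sample t-test of the mean change against -0.10. The distance is 0.9 - 0.10 = 0.80 and n = 40 x 0.9 = 36. SE = 1.41/√36 = 0.235. Noncentral t gives 91.1% power (normal approximation 92.6%), so the stated minimum of 90% is reproduced. Success needs an observed mean of about -0.58 or lower. With 52 enrolled, n = 46.8, SE = 0.206 and power is 96.7%.

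**Shift from mismatched tests.** Shift b = (fraction mismatched) x (bronchodilator effect on LCI2.5). The documents give neither factor, so both ranges are assumptions:

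- Low: 0.02 x 0.25 = 0.005
- Middle: 0.05 x 0.5 = 0.025
- High: 0.10 x 1.0 = 0.10

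In tests, 2-10% of 156 is about 3 to 16.

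**Effect on the decision.** Success means that mean + t(0.975, n-1) x SE is below -0.10. A positive b is a spurious improvement.

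| True mean change | Shift b | Success, n = 36 | Success, n = 46.8 |
|---|---|---|---|
| -0.10 | 0 | 2.50% | 2.50% |
| -0.10 | 0.025 | 3.17% | 3.28% |
| -0.10 | 0.05 | 3.98% | 4.25% |
| -0.10 | 0.10 | 6.11% | 6.88% |
| -0.10 | -0.05 (worsening) | 1.51% | 1.40% |
| 0 | 0.10 | 2.50% | 2.50% |
| +0.08 | 0.10 | 1.10% | 0.96% |
| -0.9 | -0.05 (worsening) | 87.3% | 94.5% |

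The +0.08 row is the mean placebo change that SAP 7.2 reports for Study 809-109.

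**Scale.** The middle shift is 0.025/0.80 = 3% of the planned distance to the margin, and 0.025/0.235 = 11% of one standard error. The high case is 0.10/0.80 = 12.5% of the distance. It assumes a bronchodilator effect of 1.0 unit, more than the 0.9 planned for the drug.

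**Cost of deletion.** Suppose the affected subjects lost every visit. Going from n = 36 to 34 gives 89.4% power, and to 32 gives 87.5%. The real loss is smaller, because the model keeps a subject's other visits.

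**The case for a change.** The strongest case for acting is that the gap is real in the readable text, the design has no concurrent control to absorb a shift, and the repair is cheap. Spirometry follows MBW at the same visits with the same withholding times and is recorded as pre- or post-bronchodilator, so the state of most MBW tests can be recovered. The sponsor has an interest too: if the bronchodilator effect is a worsening, a shift of 0.05 takes power at n = 36 from 91.1% to 87.3%, below the stated 90%.

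The facts and the arithmetic stand, but the need for a change does not follow:

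- **Deletion is a trade-off.** The all-data rule appears in both documents, and Protocol 11.4.1 chooses to obtain the test without rescheduling. Removing values because of bronchodilator use after baseline selects on behaviour that may track symptoms, which could itself bias a one-arm mean. With the direction unknown, the documents do not show that deletion is less biased.
- **The additions leave the result alone.** A status flag for MBW and a sensitivity model may inform a reader, but the primary estimate and the success rule stay the same. Analysts can already build both from the documented bronchodilator use and the spirometry record.
- **The power loss is conditional.** It rests on an assumed worsening. At the Table 12-1 target of 52, power in the same case is still 94.5%.
- **Unread text may cover this.** Part of Protocol 11.4.1 is redacted and MBW detail is left to the Study Reference Manual, so absence of a rule can be claimed only for what is readable.

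The modulator question is separate and comes with no magnitude. Table 9-1 states a prohibition specific to modulators, and Protocol 9.5 states a general restriction with an approval route, so the two can be read together. Completers take their last dose the evening before Week 8. Among treatment-period efficacy data, the question therefore touches only early discontinuers, whose later values the plan includes on purpose.

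**Conclusion.** The concern describes the readable text correctly but does not call for a change. Over the assumed ranges the shift is 0.005 to 0.10 LCI units against a distance of 0.80. A middle case moves one-sided error at a true change of -0.10 from 2.5% to 3.2-3.3%, and the extreme case to 6.1-6.9%. That inflation arises only if the bronchodilator effect is an improvement and the true change lies near the margin. A drug with no true change stays at or below 2.5%, and if the effect is a worsening the test becomes conservative.

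Keeping every measurement in the primary model is a fair choice, and the information needed to examine mismatched tests is largely collected already. The conclusion assumes that mismatches stay within about 10% of tests and that the bronchodilator effect does not exceed 1.0 unit, and it approximates the repeated-measures model by a one-sample t-test with SD 1.41. Mismatches well beyond 10% combined with a large effect would matter more, but nothing in the documents points to that.
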